APPENDIX H. WORK PRODUCTIVITY AND ACTIVITY IMPAIRMENT
QUESTIONNAIRE: GENERAL HEALTH V2.0(WPAI:GH).....72

LIST OF TABLES

Table 1: Study Visits.....22
Table 2: Criteria for Potentially Clinically Significant Laboratory Values.....46
Table 3: Criteria for Potentially Clinically Significant Vital Signs.....47

LIST OF ABBREVIATIONS AND DEFINITIONS OF TERMS

Abbreviation	Term
ADA	antidrug antibodies
ANCOVA	analysis of covariance
ANOVA	analysis of variance
AR (1)	the first-order autoregressive structure
β-HCG	beta-human chorionic gonadotropin
CGRP	calcitonin gene-related peptide
CH	cluster headache
CMH	Cochran-Mantel-Haenszel
CNS	central nervous system
CPRA	cumulative proportion of responder's analysis
CRF	case report form
CS	the compound-symmetry structure
CV	coefficient of variation
e-diary	electronic diary
ECG	electrocardiogram/electrocardiography
ECH	episodic cluster headache
eC-SSRS	electronic Columbia Suicide Severity Rating Scale
EOT	end of treatment
EQ-5D	EuroQol-5 Dimension
FAS	full analysis set
HADS	Hospital Anxiety and Depression Scale
IMP	investigational medicinal product
FCS	fully conditional specification
IRT	interactive response technology
ITT	intent-to-treat
iv	intravenous(ly)
LS	least square
MCS	Mental Health Composite Scores
MedDRA	Medical Dictionary for Regulatory Activities
MI	multiple imputation
MMRM	mixed model for repeated measures
NSAID	non-steroidal anti-inflammatory drug

Statistical Analysis Plan

Abbreviation	Term
PCS	Physical Composite Scores
PGIC	Global Impression of Change
PP	per-protocol
PPSI	Patient-Perceived Satisfactory Improvement
R&D	Research and Development
SAP	statistical analysis plan
sc	subcutaneous(ly)
SD	standard deviation
SE	standard error
SF-12	12-Item Short-Form Health Survey
SI	standard international
SOC	system organ class
SOP	standard operating procedure
ULN	upper limit of normal
UN	unstructured covariance
WHO Drug	World Health Organization Drug Dictionary
WPAI	Work Productivity and Activity Impairment

INTRODUCTION

This statistical analysis plan (SAP) describes the planned analysis and reporting for Teva Branded Pharmaceutical Products R&D, Inc. Study TV48125-CNS-30056, (a multicenter, randomized, double-blind, double-dummy, placebo-controlled, parallel-group study comparing the efficacy and safety of 2 dose regimens [intravenous/subcutaneous and subcutaneous] of TEV-48125 [fremanezumab] versus placebo for the prevention of episodic cluster headache), and was written in accordance with SOP GBP_RD_702.

The reader of this SAP is encouraged to read the study protocol for details on the conduct of this study, the operational aspects of clinical assessments, and the timing for completing the participation of a patient in this study.

The SAP is intended to be in agreement with the protocol, especially with regard to the primary and all secondary endpoints and their respective analyses. However, the SAP may contain more details regarding these particular points of interest, or other types of analyses (eg, other endpoints). When differences exist in descriptions or explanations provided in the study protocol and this SAP, the SAP prevails; the differences will be explained in the clinical study report.

1. STUDY ENDPOINTS

1.1. Primary Efficacy Endpoints

The primary efficacy endpoint of this study is the mean change from baseline (run-in period) in the weekly average number of cluster headache (CH) attacks during the 4-week period after administration of the first dose of the investigational medicinal product (IMP), ie, based on week 0 to 4 data.

1.2. Secondary Efficacy Endpoints

The secondary efficacy endpoints to further demonstrate efficacy are:

- the proportion of patients with a $\geq 50\%$ reduction from baseline (run-in period) in the weekly average number of CH attacks during the 4-week period after the first dose of the IMP, ie, based on week 0 to 4 data
- the mean change from baseline (run-in period) in the number of CH attacks during the 12-week period after administration of the first dose of the IMP, ie, based on week 0 to 12 data
- the mean change from baseline (run-in period) in the number of CH attacks during the 4-week period after administration of the third dose of the IMP, ie, based on week 8 to 12 data
- the mean change from baseline (run-in period) in the weekly average number of days with use of cluster-specific acute headache medications (triptans and ergot compounds) during the 12-week period after administration of the first dose of the IMP, ie, based on week 0 to 12 data
- the mean change from baseline (run-in period) in the weekly average number of days oxygen is used to treat episodic cluster headache (ECH) during the 12-week period after administration of the first dose of the IMP, ie, based on week 0 to 12 data
- assessment of patient's perceived improvement, as measured by the Patient-Perceived Satisfactory Improvement (PPSI) at 1, 4, 8, and 12 weeks after administration of the first dose of the IMP relative to baseline (day 0)

1.3. Safety Endpoints

The safety endpoints are as follows:

- occurrence of adverse events throughout the study
- clinical laboratory (serum chemistry, hematology, coagulation, and urinalysis) test results at each visit
- vital signs (systolic and diastolic blood pressure, oral temperature, and pulse rate) measurements at each visit. Note: Oxygen saturation will be measured in cases of suspected anaphylaxis and severe hypersensitivity. Respiratory rate will also be measured in these cases but not as a standard vital sign.

- 12-lead electrocardiogram (ECG) findings at screening, baseline, and week 12
- use of concomitant medication during the study
- clinically significant changes in physical examinations, including body weight
- injection site reaction (ie, erythema, induration, and ecchymosis) and injection site pain assessments
- occurrence of hypersensitivity/anaphylaxis reactions
- suicidal ideation and behavior as measured by the electronic Columbia Suicide Severity Rating Scale (eC-SSRS)

1.4. Immunogenicity Assessment Endpoints

The immunogenicity endpoints are the following:

- antidrug antibody (ADA) incidence and characteristics (eg, titer, kinetics, and neutralizing activities)

1.5. Exploratory Endpoints

The exploratory endpoints are as follows:

- █ [REDACTED]
- █ [REDACTED]
- █ [REDACTED]
- █ [REDACTED]
- █ [REDACTED]
- █ [REDACTED]
- █ [REDACTED]
- █ [REDACTED]

- █ [REDACTED]
- █ [REDACTED]
- █ [REDACTED]
- █ [REDACTED]
- █ [REDACTED]
- █ [REDACTED]
- █ [REDACTED]
- █ [REDACTED]

1.6. Wearable Sensor Substudy Endpoints

Wearable sensor substudy exploratory endpoints are the following:

- [REDACTED]
- █ [REDACTED]
- █ [REDACTED]
- █ [REDACTED]
- █ [REDACTED]
- █ [REDACTED]
- █ [REDACTED]

Statistical Analysis Plan

█ [REDACTED]

█ [REDACTED]

█ [REDACTED]

█ [REDACTED]

█ [REDACTED]

2. STUDY DESIGN

2.1. General Design

This is a 13-week, multicenter, randomized, double-blind, double-dummy, placebo-controlled, parallel-group study to compare the safety and efficacy of 2 dose regimens of fremanezumab versus placebo in adult patients for the prevention of ECH. The study will consist of a screening visit, a run-in period lasting at least 1 week (+3 days), and a 12-week double-blind treatment period. During the course of any CH attack, patients will be allowed to use acute medications to treat acute headaches, as needed.

Patients will complete a screening visit (visit 1) after providing written informed consent, and eligible patients will enter a run-in period lasting at least 1 week (+3 days) during which they will enter baseline CH attack information into an electronic diary device (e-diary) daily. Patients will return to the study center after completing the run-in period (visit 2 [week 0]). Patients who had at least 7 CH attacks during the run-in period and who continue to meet eligibility criteria (including entry of CH attack information in an e-diary demonstrating compliance for 85% of days during the run-in period) will be randomly assigned at visit 2 (week 0) in a 1:1:1 ratio to 1 of 3 treatment groups (see details in Section 2.2).

Blinded treatment will be administered once monthly (ie, approximately every 4 weeks) for a total of 3 months. Final study assessments will be performed at the final visit for this study (visit 5), approximately 12 weeks after administration of the first dose of the IMP. Upon completion of the final study assessments, early withdrawal from the study, or discontinuation for any reason, patients will be offered the opportunity to enter a 32-week long-term safety study (as described in Study TV48125-CNS-30058) for safety and ADA evaluation without additional dosing.

[figure not shown]
Patients who satisfactorily complete the study may be offered to enroll the long-term safety Study TV48125-CNS-30058 for 68 weeks (as described in this study protocol) to receive additional dosing and a final follow-up visit for safety and ADA evaluation. In any case, during the period of the long-term safety study, where patients are not receiving additional dosing (and are waiting for ADA evaluation), these patients should be treated with standard of care as appropriate. A separate protocol was issued for the long-term safety study.

CH attack information will be captured daily during the double-blind treatment period using an electronic diary device. Assessments of change in quality of life and health status (using the Hospital Anxiety and Depression Scale [HADS], EuroQol-5 Dimension [EQ-5D] questionnaire, 12-Item Short Form Health Survey [SF-12], Impact on Partner and Family questionnaire, and Work Productivity and Activity Impairment [WPAI] questionnaire); satisfaction with treatment (using the PPSI and Patients' Global Impression of Change [PGIC] scale); safety evaluations (including eC-SSRS); blood collection for pharmacokinetics, immunogenicity, biomarker, and pharmacogenomics (unless not allowed per local regulation) analyses; and urine sampling for biomarker analysis will be performed at prespecified time points.

The end of study is defined as the date the last patient attends the end of treatment (EOT)/early withdrawal visit. The study duration will be 21 months from Q4/2016 to Q2/2018.

The study schematic diagram is presented in Figure 1. Study procedures and assessments with their timing are summarized in Table 2 of the study protocol.

Figure 1: Overall Study Schematic Diagram

ECH=episodic cluster headache; IV=intravenous; PBO=placebo; SC=subcutaneous; V=visit. Note: Patients randomized to the 900-mg iv loading dose group will receive 900 mg of fremanezumab administered via an approximately 1-hour iv infusion followed by placebo as 3 sc injections at visit 2 (week 0) and fremanezumab at 225 mg administered as single sc injections (225 mg/1.5 mL) at visits 3 and 4 (weeks 4 and 8, respectively). Patients randomized to the fremanezumab 675-mg sc quarterly group will receive placebo administered via an approximately 1-hour iv infusion followed by fremanezumab at 675 mg administered as 3 sc injections (225 mg/1.5 mL) at visit 2 (week 0) and placebo administered as single sc injections at visits 3 and 4 (weeks 4 and 8, respectively). Patients in the placebo group will receive placebo administered via an approximately 1-hour iv infusion followed by placebo administered as 3 sc injections at visit 2 (week 0) and placebo administered as single sc injections at visits 3 and 4 (weeks 4 and 8, respectively).

2.1.1. Wearable Sensor Substudy

A subset of patients in selected investigational sites will be offered to participate in a substudy to understand the [REDACTED]

Patients who are able to demonstrate appropriate use of the wearable device and are willing to comply with the requirements for use of the digital wearable device will be given the device and accessories at the baseline visit. The device will be worn continuously throughout the 12-week treatment period, and for patients who continue into the long-term safety study (Study TV48125-CNS-30058), the device will be worn continuously throughout the 40-week treatment period of that study. Refer to Section 8.6 of the study protocol for additional details.

2.2. Randomization and Blinding

Patients will be randomly assigned with stratification based on gender, country, and baseline concomitant preventive medication use (yes or no) in a 1:1:1 ratio to 1 of 3 treatment groups.

- **fremanezumab 900-mg intravenous (iv) loading dose group:** fremanezumab at 900 mg administered via a 1-hour iv infusion and 3 subcutaneous (sc) placebo injections at visit 2 followed by fremanezumab at 225 mg administered as single sc injections (225 mg/1.5 mL) at visits 3 and 4
- **fremanezumab 675-mg sc quarterly group:** fremanezumab at 675 mg administered as 3 sc injections (225 mg/1.5 mL) and a 1-hour placebo iv infusion at visit 2 followed by placebo administered as single sc injections at visits 3 and 4
- **placebo group:** placebo administered via a 1-hour iv infusion and as 3 sc injections at visit 2 followed by placebo administered as single sc injections at visits 3 and 4

The sponsor, investigators, study staff (except for staff involved in bioanalytical analyses and interim analyses [by a third-party, unblinded statistician]), and patients will be blinded to treatment assignment throughout the study.

Randomization will be performed using electronic interactive response technology (IRT), a third-party vendor. The randomization code will be generated by IRT following specifications from the Biostatistics Department. A Teva statistician will be responsible for reviewing the dummy randomization codes, and the final randomization code will be maintained by the third-party vendor in a secure location.

2.3. Data Monitoring Committee

Not applicable.

2.4. Sample Size and Power Considerations

[REDACTED]

2.5. Sequence of Planned Analyses

2.5.1. Planned Interim Analyses

An interim analysis for fertility evaluation will be performed once 50% of patients (the first 150 patients) have completed 4-week assessments during the double-blind study period or have withdrawn from the study early. An independent statistician from a third party will perform evaluation.

Details are provided in the separate interim analysis plan.

2.5.2. Final Analyses and Reporting

All analyses identified in this SAP will be performed after the final database lock for study completion or for early termination of study as result of fertility evaluation at interim analysis.

3. ANALYSIS SETS

3.1. Intent-to-Treat Analysis Set

The intent-to-treat (ITT) analysis set will include all randomized patients.

In the ITT analysis set, treatment will be assigned based on the treatment to which patients were randomized, regardless of which treatment they actually received.

3.2. Safety Analysis Set

The safety analysis set will include all randomized patients who receive at least 1 dose of the IMP.

In the safety analysis set, treatment will be assigned based on the treatment patients actually received, regardless of the treatment to which they were randomized, unless otherwise specified.

3.3. Full Analysis Set

The full analysis set (FAS) will include all patients in the ITT analysis set who receive at least 1 dose of the IMP and have at least 10 days of postbaseline efficacy assessment in the first 4-week on the primary endpoint.

In the FAS, treatment will be assigned based on the treatment to which patients were randomized, regardless of which treatment they actually received.

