9.2.3. Full Analysis Set

The full analysis set will include all patients in the ITT analysis set who receive at least 1 dose of IMP and have at least 1 postbaseline efficacy assessment on the primary endpoint.

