9.5.4. Planned Method of Analysis

The full analysis set (see Section 9.2.3) will be used for all efficacy analyses. Summaries will be presented by treatment group.

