6. EFFICACY ANALYSIS

6.1. General

The FAS will be used for all efficacy analyses unless otherwise noted. Analyses of the primary and secondary endpoints will be repeated for the PP analysis set [REDACTED].

For data not collected daily, baseline is the last observed data before the administration of the first dose of the IMP. For data collected daily in the e-diary, baseline will be derived from the run-in period (including days from the informed consent up to the day prior to the first dose of the IMP administration). Details are provided in Section 6.1.3. The efficacy baseline value derived from the run-in period are

- number of CH attacks
- number of CH attacks of at least severe severity
- number of days with use of cluster-specific acute headache medication (triptans and ergot compounds)
- number of days with use of any acute headache medication
- number of days oxygen is used
- severity of CH attacks

Summaries will be presented by treatment group as randomized unless otherwise noted. In addition to inferential statistics, descriptive statistics will be presented by-visit or by-analysis-window summaries.

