6.1.4.1. Primary Efficacy Endpoint

The weekly average number of CH attacks during the 4-week period will be calculated based on data available and prorated to 7 days using formula [1]. Note, patients who have < 10 days of e-diary data in the first 4-week will be excluded from FAS and PP analysis set (Section 3).

As sensitivity analyses, the primary endpoint will be analyzed using the following methods for handling missing data :

- Multiple imputation (MI) method to impute missing weekly data
- An mixed model for repeated measures (MMRM) method to analyze the weekly data

Detail is provided in Section 6.2.3.

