6.1.4.2. Analyses Based on Monthly and 12-week Window

[REDACTED]

[REDACTED]

- [REDACTED]
- [REDACTED]

[REDACTED]

- [REDACTED]
- [REDACTED]

[REDACTED]

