6.3. Secondary Efficacy Endpoints and Analyses

The secondary efficacy endpoints are listed in Section 1.2. Analyses will be based on the FAS and PP analysis sets [REDACTED].

As exploratory analyses, endpoints analyzed using an ANCOVA method will be also analyzed using MMRM method in a manner analogous to the analysis as described in Section 6.2.3.2. The analysis windows will be specified in the related section.

6.3.1. Proportion of Patients with a $\geq 50\%$ Reduction from Baseline in the Weekly Average Number of CH Attacks During the 4-Week Period After the First Dose of the IMP

This secondary efficacy endpoint will be analyzed using Cochran-Mantel-Haenszel (CMH) test stratified by baseline preventive medication use (yes or no). Descriptive statistics (count and percent) and p-value for Row Mean Scores difference will be presented.

CH attacks will be derived from the e-diary data as described in Section 6.1.1. The analysis will be based on weeks 1 to 4 analysis window which will be derived using the algorithm described in Section 6.1.3. The weekly average number of CH attacks will be calculated based on data available and prorated to 7 days using formula [1]. Missing data handling methods are provided in Section 6.1.4.2.

The proportion of reduction for a patient will be calculated using formula [2]. Responders will be those with $\geq 50\%$ reduction.

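### The SAP narrows the full analysis set from 1 post-baseline assessment to 10 diary days while SAP 16 reports no changes; on the visible text, the earliest leavers fall out of the responder analysis

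*SAP*

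**What the plan says.** **Protocol.** Section 9.2.3 admits to the full analysis set (FAS) those randomised patients who "receive at least 1 dose of IMP and have at least 1 postbaseline efficacy assessment on the primary endpoint". Section 9.5.4 adds: "The full analysis set (see Section 9.2.3) will be used for all efficacy analyses". For responder analyses, section 9.3.1 counts early terminators as non-responders; completers with intermittent missing diary days have their data prorated.

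**SAP, analysis set.** Section 3.3 keeps the one-dose condition but requires that patients "have at least 10 days of postbaseline efficacy assessment in the first 4-week on the primary endpoint". Section 6.1.4.1 repeats this as an exclusion: "patients who have < 10 days of e-diary data in the first 4-week will be excluded from FAS and PP analysis set".

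**SAP, where the set is used.** Section 6.1: "The FAS will be used for all efficacy analyses unless otherwise noted". Section 6.3, on the secondary endpoints: "Analyses will be based on the FAS and PP analysis sets", with the rest of the sentence redacted. Section 6.3.1 computes the responder rate from available data prorated to a week and then says: "Missing data handling methods are provided in Section 6.1.4.2". The body of that section is redacted, as is all of SAP 3.5.

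**SAP, changes.** Section 16, on changes from the protocol's analyses, reads 'None'. The SAP Introduction says that the SAP prevails where the documents differ and that the clinical study report will explain the differences.

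**The concern.** Two things follow, with different degrees of certainty.

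The first is certain. The entry condition for the main efficacy set has changed, and the section meant to list such changes denies that any exist. Someone who relies on SAP 16 would assume that the protocol's FAS still applies.

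The second is probable. A patient outside the FAS cannot be counted as a failure in an FAS analysis. On the visible text, a dosed patient who terminates early with 1 to 9 diary days therefore leaves the responder denominator, whereas the protocol's FAS and its non-responder rule together would keep that patient as a failure. The set is then defined by data observed after randomisation. The protocol names lack of efficacy as a reason for withdrawal (3.4 and 4.3), so early loss need not be unrelated to outcome.

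The primary endpoint is partly covered, because its multiple-imputation sensitivity analysis (SAP 6.2.3.1) uses the intent-to-treat set. No comparable analysis is visible for the responder endpoint.

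**Working it through.** **The plan's own figure.** Protocol 9.1 gives 86 completers per arm, difference 1, SD 2, two-sided alpha 0.05, power at least 90%, 14% discontinuation and about 300 randomised.
- Normal approximation: n = 2 × (1.960 + 1.282)² × 2² / 1² = 84.1, so 85 per arm. The t-test has power 0.8999 at 85 and 0.903 at 86, so 86 reproduces.
- 258 / (1 − 0.14) = 300.

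**Who is affected.**

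| Dosed patient | Protocol 9.2.3 with 9.3.1 | SAP 3.3 with 6.1 and 6.3 (visible text) |
|---|---|---|
| No post-baseline diary day | outside FAS | outside FAS |
| Terminates early, 1–9 diary days | in FAS, non-responder | outside FAS |
| Terminates early, 10 or more days in the first 4 weeks | in FAS, non-responder | in FAS; handling in redacted 6.1.4.2 |
| Stays in, 1–9 days in the first 4 weeks | in FAS; non-responder rule does not apply | outside FAS |

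The conflict with the non-responder rule is confined to the second row. The table treats one diary day as one assessment on the primary endpoint. That is the natural reading, but the protocol does not say so.

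**How many.** The documents give no count, so these are assumptions built on the 14% figure:
- Loss spread evenly over 84 days: 14 × 9/84 = 1.5 per 100 leave in days 1–9 (42 × 9/84 = 4.5 of 300).
- Half the loss in the first 28 days: 7 × 9/28 = 2.25 per 100.
- All the loss in the first 28 days: 14 × 9/28 = 4.5 per 100.

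**Effect on the estimate.** Assume 50 versus 40 responders per 100 (active, placebo), with every excluded patient a non-responder. The difference is 10.0 points with nobody excluded.
- 2 excluded from each arm: 50/98 − 40/98 = 10.2 points.
- 2 from active only: 50/98 − 40/100 = 11.0 points.
- 2 from placebo only: 50/100 − 40/98 = 9.2 points.

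**Effect on the test.** The single-stratum Cochran-Mantel-Haenszel statistic is (a − n₁m/N)² / [n₁n₂m(N − m) / (N²(N − 1))], where a is the number of responders on active, m all responders, n₁ and n₂ the arm sizes and N their sum. For 53/98 versus 40/100: n₁m/N = 98 × 93/198 = 46.03, the variance is 12.39, and the statistic is 6.97²/12.39 = 3.92, giving p = 0.048.

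| Responders per 100 | Excluded (active/placebo) | p |
|---|---|---|
| 53 vs 40 | 0/0 | 0.066 |
| 53 vs 40 | 2/2 | 0.064 |
| 53 vs 40 | 2/0 | 0.048 |
| 54 vs 40 | 0/0 | 0.048 |
| 54 vs 40 | 2/2 | 0.046 |
| 54 vs 40 | 0/2 | 0.064 |

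Balanced loss of this size hardly moves the p-value; one-sided loss can carry it across 0.05 in either direction.

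**How often.** With equal early-loss rates, two arms of 100 differ by 2 or more exclusions by chance in 36% of trials at 1.5 per 100 and 60% at 4.5 per 100 (two independent binomials).

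Simulation of 400,000 trials, 100 per arm, excluded patients all non-responders, comparing all dosed patients with the 10-day set:
- True rates 54% and 40%: the decision at 0.05 differs in 3.7% of trials at 1.5 per 100 and 6.5% at 4.5 per 100, in both directions. At 1.5 per 100, rejection is 52.9% with all dosed and 51.7% with the 10-day set.
- True rates 40% and 40%, 1.5 per 100: decisions differ in about 0.9% of trials; rejection is 0.051 and 0.050.

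**Why a minimum is reasonable for the primary endpoint.** At one attack a day with Poisson counts (assumption), a prorated weekly value has SD 7 × √(1/d): 7.0 from 1 day, 2.2 from 10 days and 1.3 from 28 days, against a planned SD of 2.

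**The case against.** The consequential half rests on text that cannot be seen. SAP 3.5 sits under the heading for analysis sets and is wholly redacted. So is the section cited for this endpoint's missing data, and the population sentences in 6.1 and 6.3 end in redactions. Section 6.1 also allows for exceptions. A further set or rule that restores these patients may be there, and redacted text is not absent text. This objection stands. It limits the responder consequence to a conditional finding, but it does not touch the inaccuracy of SAP 16.

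The 10-day rule is also stated openly, twice. Protocol section 9 leaves changes to the SAP, 9.16 lets deviations be described in an amendment, the SAP or the study report, and the SAP Introduction gives the SAP precedence. A reader might infer concealment; the documents do not support that. These clauses make the 10-day rule operative, but they do not make 'None' correct.

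A reader might also infer that the SAP abolishes the non-responder rule. It does not visibly do so. Under the protocol, too, that rule works inside the FAS; the conflict arises only through membership, and nothing visible repeals the rule for early terminators who remain in the set. Nor does the rule cover patients who stay in with few diary days, so their exclusion does not breach it.

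Finally, 54% versus 40% has power near one half, where changed decisions are most frequent, and a fixed 0.05 threshold simplifies the planned Hochberg procedure. Both points are fair and are reflected in the size given below.

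**Conclusion.** The change to the FAS is real and SAP 16 misreports it; that part does not depend on any redacted text. That the earliest leavers drop out of the responder analysis is probable, and conditional on SAP 3.5, 6.1.4.2 and the cut-off population sentences adding nothing.

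If so, the effect is likely to be small and its direction cannot be predicted. It matters when early loss is uneven between arms and the result lies near the boundary. A reader might infer inflated type I error or a tilt towards the drug; the calculations show neither. These sizes rest on assumed early-loss rates, assumed responder rates and all excluded patients being non-responders, because the documents give none of these.

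SAP 16 also omits other visible differences:
- per-protocol membership: no important deviations in protocol 9.2.4; completers without eligibility or dosing violations in SAP 3.4;
- per-protocol treatment assignment: as received in the protocol, as randomised in the SAP;
- region: US or other in protocol 9.5.4.1; US/Canada or other in SAP 4.3;
- baseline comparisons: tests in protocol 9.4.2; none in SAP 5.3.

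These are disclosure gaps, and no bias is claimed from them.

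**What to change.** 1. **SAP 6.3.1.** Unless the redacted text already does this, analyse the responder endpoint on the FAS of protocol 9.2.3, by randomised treatment, counting early terminators as non-responders as in protocol 9.3.1. Show the 10-day result as a sensitivity analysis. State the rule for patients who stay in with fewer than 10 diary days. An all-dosed version is optional; it is slightly wider than the protocol's set because it adds dosed patients with no post-baseline diary data.
2. **Primary endpoint.** Keep the 10-day rule for the ANCOVA. Report the number excluded and the reasons, by arm, beside the planned intent-to-treat multiple-imputation result.
3. **SAP 16, before unblinding.** Replace 'None' with the FAS change, and list the per-protocol, region and baseline-test differences as disclosure items. Add to SAP 3.4 the 10-day per-protocol condition that now stands only in 6.1.4.1.

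The cost is SAP wording, one more responder table and an exclusion count by arm. Responder rates will be slightly lower in each arm. No new data are needed, and the primary analysis gains no noise because its entry rule is unchanged.
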